#### **Parameters with NCI-CTC grades available:**

The laboratory toxicities will be tabulated using descriptive statistics (number of patients and percentages) during the on-treatment period. The denominator to calculate percentages for each laboratory parameter is the number of patients evaluable for CTCAE grading (ie, those patients for whom a Grade 0, 1, 2, 3 or 4 can be derived).

- The summary of laboratory parameters by CTCAE grade table will include number and percentage of patients with Grade 1, 2, 3, 4, Grade 3/4 and any grade (Grades 1-4), laboratory abnormalities during the on-treatment period.
- The shift table will summarize baseline CTCAE grade versus the worst on-treatment CTCAE grade. The highest CTCAE grade during the on-treatment period is considered as the worst grade for the summary.

The above analyses apply to hematology and chemistry evaluations which can be graded per CTCAE, ie:

- Hematology:

Hemoglobin (HB), Leukocytes (white blood cell decreased), Lymphocytes (lymphocyte count increased/decreased), Neutrophils / Absolute Neutrophils Count (ANC) (neutrophil count decreased), Platelet Count (PLT) (platelet count decreased), Coagulation (activated partial thromboplastin time (aPTT) and prothrombin time (INR)).

- Serum Chemistry:

Albumin (hypoalbuminemia), Alkaline Phosphatase (alkaline phosphatase increased), Alanine Aminotransferase (ALT) (ALT increased), Amylase (serum amylase increased), Aspartate Aminotransferase (AST) (AST increased), Total Bilirubin (blood bilirubin increased), Cholesterol (cholesterol high), Creatinine (creatinine increased), Creatine Kinase (CPK increased), Potassium (hypokalemia/ hyperkalemia), Sodium (hyponatremia/ hypernatremia), Magnesium (hypomagnesemia/hpermagnesemia), Calcium (hypocalcemia/ hypercalcemia), Glucose (hypoglycemia/hyperglycemia), Gamma Glutamyl Transferase (GGT) (GGT increased), Lipase (lipase increased), Phosphates (hypophosphatemia), Triglycerides (hypertriglyceridemia).

**Parameters with NCI-CTC grades not available:**

Hematology and chemistry evaluations which cannot be graded per CTCAE criteria will be summarized as frequency (number and percentage) of patients with:

- shifts from baseline normal to at least one result above normal during on-treatment period.
- shifts from baseline normal to at least one result below normal during on-treatment period.

In this study, these apply to the following parameters:

- Hematology: Absolute Monocytes, Absolute Eosinophils, Absolute Basophils.
- Serum Chemistry: Chloride, Total Urea, Uric Acid, Total Protein, C-Reactive Protein, Lactate Dehydrogenase (LDH).

**6.6.5.2. Other Laboratory Parameters**

All other parameters collected on the eCRF will be listed in dedicated listings presenting all corresponding collected information on the eCRF.

- Urinalysis: all urinalysis parameters (except for Proteinuria, which will be summarized with CTCAE grades).

- Other parameters: hormone, and immunology parameters.
- Pregnancy test.

The listings of laboratory results will be provided for all laboratory parameters. The listings will be sorted by parameters and assessment dates or visits for each patient. Laboratory values that are outside the normal range will also be flagged in the data listings, along with corresponding normal ranges. A listing of CTCAE grading will also be generated for those laboratory tests.

In addition, listings of abnormal values will be provided for hematology, chemistry, urinalysis, coagulation parameters. If there is at least one abnormal assessment for any parameter, all the data for that laboratory parameter will be included into the listing.

For all tests not mentioned above but present in the clinical data, a listing of patients with at least one result for the relevant test will be provided.

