32. **Follow Up:** Patients should be evaluated up to 90 days after last dose of study treatment. Refer to the protocol for specific guidelines. Patients continuing to experience toxicity following discontinuation of study treatment will continue to be followed at least every 4 weeks until resolution or determination, in the clinical judgment of the Investigator, that no further improvement is expected. PK and immunogenicity samples should be collected as described in the PK and Immunogenicity Assessment section in Schedule of Activities ([Table 3](#)). Patients whose disease has not progressed at the end of treatment will enter into disease follow-up. During this follow-up period, patients will have disease assessments performed every 12 weeks \pm 7-days. Once patients have exhibited disease progression or began a new anti-cancer therapy, or 6-month follow-up from the date of the first dose of the last enrolled patient, whichever occurs first, they will be withdrawn from the study. See [Section 4.3.1](#) Contraception for guidelines on contraception checks during this period.
33. **De novo tumor biopsy for biomarker assessment (Dose escalation):** For patients in dose-escalation cohorts, unscheduled optional de novo tumor biopsies may be collected at the discretion of the investigator and sponsor to support the assessment of disease progression.
34. **De novo tumor biopsy for biomarker assessment (Expansion cohorts):** Mandatory for patients in expansion cohorts only. A de novo biopsy will be required at study entry followed by a second biopsy at the time of the Week 9 scans (after 3 cycles of treatment).
35. **Continued Treatment Beyond Cycle 8:** This will be on a reduced visit schedule (Day 1 of each cycle), or as clinically indicated.
36. **Thyroid Function Tests:** To be collected every 2 cycles for the first 8 cycles, and then every 4 cycles (Cycles 1, 3, 5, 7, 11, 15 etc.).
37. **Hepatitis B and C Tests:** Conduct tests for hepatitis B surface antigen, core antibody, and anti-hepatitis C. Other tests may be conducted per standard practice to confirm an active hepatitis infection.

Table 4. Required Laboratory Tests

SAFETY LABORATORY REQUIREMENTS	
Refer to the Schedule of Activities table for specific timepoints and instructions	
Assessments	
Hematology Panel:	Chemistry Panel:
Absolute Neutrophil Count	Sodium
Hemoglobin	Potassium
	Total Calcium
Platelet Count	Creatinine
WBC with differential (5-part if available)	Albumin

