2.2. Endpoints

Primary Endpoint

- First 2 cycles Dose-Limiting Toxicity (DLT) of PF-05082566 in combination with MK-3475.

Secondary Endpoints

- Adverse events as characterized by type, frequency, severity (as graded by NCI CTCAE v.4.03), timing, seriousness and relationship to study therapy PF-05082566 in combination with MK-3475;

- Laboratory abnormalities as characterized by type, frequency, severity (as graded by NCI CTCAE v.4.03);
- Vital signs, weight, ECOG Performance Status;
- PK parameters of PF-05082566 and MK-3475, including but not limited to C_{max} , C_{trough} , T_{max} , AUC_{0-last} , $AUC_{0-\infty}$, CL and Vd (as data permits);
- Anti-Drug Antibody levels for PF-05082566 and MK-3475;
- Objective tumor response by Response Evaluation Criteria in Solid Tumors (RECIST) v1.1;
- Time-to-response (expansion cohorts only);
- Duration of response (expansion cohorts only);
- Progression-free survival (expansion cohorts only);
- **Expansion Cohorts Only:** Paired de novo tumor biopsy collection at sequential time points for analysis of exploratory mechanistic biomarkers such as IHC assessment of tumor-infiltrating lymphocytes, quantitation of T cell receptor sequences, and gene expression.

CCI

- CCI

- CCI

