7.1.2.1. MK-3475 Adverse Events of Special Interest

Selected non-serious and serious AEs are also known as Events of Clinical Interest (ECI) and must be recorded as such on the Adverse Event case report forms and reported within 24 hours to the Sponsor either by electronic media or paper.

ECIs for this trial include:

1. An overdose of Sponsor's product, as defined in [Section 8.4](#) - Medication Errors, that is not associated with clinical symptoms or abnormal laboratory results.
2. An elevated AST or ALT lab value that is greater than or equal to 3X the upper limit of normal and an elevated total bilirubin lab value that is greater than or equal to 2X the upper limit of normal and, at the same time, an alkaline phosphatase lab value that is less than 2X the upper limit of normal, as determined by way of protocol-specified laboratory testing or unscheduled laboratory testing.

Note: These criteria are based upon available regulatory guidance documents. The purpose of the criteria is to specify a threshold of abnormal hepatic tests that may require an additional evaluation for an underlying etiology. The trial site guidance for assessment and follow up of these criteria can be found in the Investigator Trial File Binder (or equivalent).

3. In the event a patient develops any of the following AEs, a detailed narrative of the event should be reported as an ECI to the Sponsor within 24 hours of the event:
 - a. Grade ≥ 3 diarrhea;
 - b. Grade ≥ 2 colitis;
 - c. Grade ≥ 2 pneumonitis;
 - d. Grade ≥ 3 hypo- or hyperthyroidism.

A separate guidance document has been provided entitled “Event of Clinical Interest and Immune-Related Adverse Event Guidance Document.” This document can be found in the administrative binder and provides guidance regarding identification, evaluation and management of ECIs and irAEs. Additional ECIs are identified in this guidance document and also need to be reported to the SPONSOR within 24 hours of the event.

Patients should be assessed for possible ECIs prior to each dose. Laboratory results should be evaluated and patients should be asked for signs and symptoms suggestive of an immune related event. Patients who develop an ECI thought to be immune-related should have additional testing to rule out other etiologic causes. If laboratory results or symptoms

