7.1.3. Laboratory Safety Assessment

Hematology, blood chemistry, coagulation and urinalysis will be carried out at the time points described in the Schedule of activities (see the [Schedule Of Activities](#) and [Table 4](#)) and analyzed at local laboratories. Thyroid function assessments will include T3, FT4, and thyroid stimulating hormone (TSH). In the presence of clinical suspicion of hypopituitarism or hypoadrenalism, laboratory testing should include one or both of the following: adrenocorticotrophic hormone (ACTH) and cortisol levels before and 30-60 minutes after corticotrophin stimulation. Urinalysis will include measurement of pH, specific gravity, protein/albumin, glucose, blood/hemoglobin, ketones/acetone. Urine dipstick for urine protein: if positive collect 24-hr and microscopic (Reflex Testing). Urine dipstick for urine blood: if positive collect a microscopic (Reflex Testing).

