8.5. Abnormal Test Findings

The criteria for determining whether an abnormal objective test finding should be reported as an AE are as follows:

- Test result is associated with accompanying symptoms; and/or
- Test result requires additional diagnostic testing or medical/surgical intervention; and/or
- Test result leads to a change in study dosing (outside of protocol-stipulated dose adjustments) or discontinuation from the study, significant additional concomitant drug treatment, or other therapy; and/or
- Test result is considered to be an adverse event by the investigator or sponsor.

Merely repeating an abnormal test, in the absence of any of the above conditions, does not constitute an AE. Any abnormal test result that is determined to be an error does not require reporting as an AE.

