9.6.2.2. Laboratory Test Abnormalities

The number and percentage of patients who experienced laboratory test abnormalities will be summarized according to worst toxicity grade observed for each lab assay. The analyses will summarize laboratory tests both on the entire study period and by cycle (Cycle 1, Cycle 2, and Cycles beyond 2).

For laboratory tests without CTC grade definitions, results will be categorized as normal, abnormal or not done.

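### The SAP only lists the scheduled thyroid tests, so thyroid laboratory abnormalities that are not reported as adverse events appear in no count by treatment group

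*SAP*

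**What the plan says.** Table 2 of the protocol puts T3, FT4 and TSH at screening, on treatment cycles and at End of Treatment. Footnote 36 of the Schedule of Activities gives the frequency: "To be collected every 2 cycles for the first 8 cycles, and then every 4 cycles". Table 4 includes them among the required tests, in an entry separate from the hematology and chemistry panels. Section 7.1.2.1 names Grade 3 or higher "hypo- or hyperthyroidism" as an event of clinical interest.

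Protocol 2.2 makes frequency part of the laboratory secondary endpoint. Protocol 9.6.2.2 plans counts and percentages of patients by worst grade, assay by assay, and then adds: "For laboratory tests without CTC grade definitions, results will be categorized as normal, abnormal or not done". Hormone tests are not excepted.

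SAP 6.6.5.1 covers hematology and chemistry. It tabulates a named set of gradable tests and a second named set of ungraded tests, the latter as shifts from a normal baseline to at least one high or low on-treatment result. SAP 6.6.5.2 takes the remainder: "All other parameters collected on the eCRF will be listed in dedicated listings presenting all corresponding collected information on the eCRF". One item under that rule reads "Other parameters: hormone, and immunology parameters".

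**The concern.** The trial selects a dose of a combination, and one partner drug has thyroid dysfunction among its named events. The thyroid panel is collected repeatedly in every patient, yet no planned laboratory table states how many patients per treatment group moved out of the normal range. Such a figure would not depend on whether the investigator judged the finding reportable.

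The adverse-event tables fill the gap only in part. Under Protocol 8.5 an abnormal result is reported as an adverse event when it comes with symptoms, needs further testing or intervention, leads to certain changes in dosing or treatment, or is judged an event by the investigator or sponsor. The section adds: "Merely repeating an abnormal test, in the absence of any of the above conditions, does not constitute an AE". An abnormal TSH that meets none of the criteria is therefore in a listing and in no count.

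Baseline status also matters. Exclusion criterion 18 admits patients whose hypothyroidism is stable on replacement, so a crude count of out-of-range values would mix long-standing with new abnormality. A shift from a normal baseline is the SAP's own device for dealing with this, but it is not applied to these tests.

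**Working it through.** The plan gives no figure to reproduce. The check is a comparison of text, plus one count.

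**1. Where thyroid results appear in the SAP's laboratory outputs**

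| Output | Scope | T3, FT4 or TSH? |
|---|---|---|
| Grade tables and grade shifts (6.6.5.1) | named hematology, coagulation and chemistry tests | no |
| Normal-to-abnormal shifts, ungraded tests (6.6.5.1) | monocytes, eosinophils, basophils; chloride, urea, uric acid, total protein, C-reactive protein, LDH | no |
| Listing of all laboratory results (6.6.5.2) | every parameter, by patient and date, out-of-range values flagged | yes |
| Listings of abnormal values (6.6.5.2) | hematology, chemistry, urinalysis, coagulation | not named |

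A general sentence in 6.6.5.1 promises below, within or above normal for results outside the CTCAE. It does not bring the thyroid tests in. It stands under the hematology and chemistry heading, the list of ungraded parameters that follows is closed, and 6.6.5.2 assigns hormones elsewhere by name. The number of planned laboratory tables that count thyroid abnormalities is therefore zero.

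**2. Whether the selection follows the tests this protocol requires**

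Chloride and C-reactive protein receive shift summaries, and amylase, lipase, cholesterol and triglycerides receive grade tables. None of these six is in protocol Table 4. The thyroid panel is in Table 4 and receives neither.

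**3. Whether the departure is explained**

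The SAP's summary of changes mentions the laboratory section only for denominators. It says nothing about hormone tests. SAP 3.2.1 restates the laboratory endpoint without the word frequency, but the SAP still gives frequencies for the other tests, so this does not account for the omission.

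**4. How many panels are involved**

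Footnote 36 gives Cycles 1, 3, 5, 7, 11, 15 and onward in steps of four. Through Cycle 32 these are 1, 3, 5, 7 (4 panels) and 11, 15, 19, 23, 27, 31 (6 panels), so 4 + 6 = 10. The footnote does not say whether the Cycle 1 sample is drawn before dosing. If it is (assumption), it serves as baseline under SAP 3.4.1 and 10 − 1 = 9 post-baseline panels remain; otherwise 10. The End of Treatment panel, at about 28 days after the last dose, comes on top. It falls within the SAP's 30-day on-treatment period unless a new anti-cancer drug has started.

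**5. What is counted and what is not**

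- Abnormal result reported as an adverse event: counted by treatment group in the adverse-event tables (SAP 6.6.1), and in the immune-related tables (SAP 6.6.4) if it is on the search list.
- Abnormal result meeting no criterion in Protocol 8.5: flagged in the listing, in no count.

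**The case against.** The strongest reply is that nothing is hidden and nothing is forbidden.

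- Protocol section 9 and SAP section 2 both let the SAP modify the protocol's plans; only major changes to the primary endpoint need an amendment. This stands. A reader might infer that the SAP breaches the protocol, and the documents do not support that.
- Protocol 9.6.2.2 asks for categories for ungraded tests, not for a baseline shift or a breakdown by dose, and a flagged listing is a kind of categorisation. This stands in part. The by-group layout comes from SAP 5.2. But the sentence sits in a section on numbers and percentages of patients, and a not-done category fits a table better than a listing.
- A reader might infer that listings cannot separate new from pre-existing dysfunction. That is too strong. Values are listed by patient and date with normal ranges, and medical history and concomitant medications are reported. With at most 45 patients in escalation, tracing by hand is workable, though the size of the expansion is open. What the listings lack is a count.
- A reader might equate any biochemical shift with the named event, or infer that the tests were scheduled because of it. The named event is Grade 3 or higher only, and no section gives the reason for the schedule.
- Protocol 7.1.2.1 requires review for possible events of clinical interest before each dose, and extra testing where results suggest an immune-related one. Extra testing is itself an adverse-event criterion in 8.5. This narrows the gap to abnormalities that prompt no work-up, treatment or dosing change and are not judged to be events. It does not close it.

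**Conclusion.** The point holds as a reporting gap. Required, scheduled thyroid tests are moved from the protocol's summarised results to listings without explanation, and abnormalities that are not reported as adverse events are in no count by treatment group. It would be wrong to conclude that thyroid dysfunction goes unreported: values are listed with flags, and thyroid adverse events are tabulated.

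The size is modest. The primary endpoint, the MTD estimate and the sample size are untouched. The 9 or 10 post-baseline panels per patient are a ceiling that needs a full 32 cycles. They show how much data is collected, not how many abnormalities would be missed, and the documents give no rate from which to estimate that. The conclusion assumes that the three tests are handled as ungraded hormone parameters, which is how the SAP's lists treat them.

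**What to change.** Add TSH, FT4 and T3 to the SAP 6.6.5.1 shift summary for ungraded parameters: patients with a normal baseline and at least one on-treatment result above normal, and likewise below normal, by treatment group. Use the number of patients tested for that analyte as the denominator and print it, which also shows how many were not tested. Remove these three tests from the listing-only rule in 6.6.5.2 and keep the listing. If listing only is intended, state that as a departure from Protocol 9.6.2.2 and give the reason.

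A combined count, such as high TSH together with low FT4, is optional. Neither document defines it, so its definition would have to be fixed before the analysis.

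The cost is a few lines of SAP text and one more table from data already collected. No visit, sample or aspect of patient management changes.

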#### **6.6.6. Vital Signs**

Weight for the purposes of dose calculation will be recorded at screening and within 3 days pre-dose Day 1 of each cycle. Weight will not be collected at End of Treatment. Height will be measured at screening only.

Vital sign summaries will include all vital sign assessments from the on-treatment period. All vital sign assessments will be listed, and those collected outside the on-treatment period will be flagged in the listing.

All vital sign parameters will be summarized using descriptive statistics (mean, SD, median, Q1, Q3, minimum, and maximum) of actual values and changes from baseline for each visit over time. End of Treatment visit will be summarized separately. The changes computed will be the differences from baseline.

#### **6.6.7. Electrocardiogram**

ECG summaries will include all ECG assessments from screening and the on-treatment period. All ECG assessments will be listed, and those collected outside the on-treatment period will be flagged in the listing. QTcB and QTcF will be derived based on HR and QT (see below). The average of the replicate measurements should be determined after the derivation of the individual parameter at each time point.

#### **Selecting Primary QT Correction for Heart Rate**

The analysis of QT data is complicated by the fact that the QT interval is highly correlated with heart rate. Because of this correlation, formulas are routinely used to obtain a corrected value, denoted QTc, which is independent of heart rate. This QTc interval is intended to represent the QT interval at a standardized heart rate. Several correction formulas have been proposed in the literature. For this analysis we will use some of those methods of correction, as described below. The QT interval corrected for heart rate by the Bazett's formula, QTcB, is defined as:

$$QTcB = \frac{QT}{\sqrt{RR}},$$

the QT interval corrected for heart rate by the Fridericia's formula, QTcF, is defined as

$$QTcF = \frac{QT}{\sqrt[3]{RR}},$$

where RR represents the RR interval of the ECG, in seconds, and can be estimated as 60/Heart Rate.

Both formula produce similar results when the range of heart rates is not extreme. If QTcB and QTcF methods do not adequately correct QT for heart rate, an empirical correction specific to the study population can be derived.

These corrections were obtained by starting with the simple power model:

$$QT = a \times RR^b \quad (1)$$

and then used the natural log transformation to derive the equation:

$$\ln(QT) = \ln(a) + b \ln(RR) \quad (2)$$

The power model can be used to derive an empirical correction based on the reference group by fitting a linear mixed-effects regression model to the  $\ln(QT)$  and  $\ln(RR)$  data, estimating the slope  $b$  from Equation 2, and then applying that as a power in  $QTcP(\text{msec}) = QT(\text{msec})/RR(\text{sec})^b$  to correct all the singlet data (on-drug as well as off-drug.)

Data will be summarized using QTcF and QTcB. However, if these are not appropriate correction method for the data set, the results will also be summarized using QTcP.

